7.1.6 EQ-5D-5L Change at 3 Months

The EuroQol 5-Dimension 5-Level (EQ-5D-5L) is a generic preference-based questionnaire developed by the EuroQol Group to measure health-related quality of life. The EQ-5D-5L measures quality of life across 5 domains: mobility, self-care, usual activities, pain/discomfort, and anxiety/depression. Each dimension is scored on a 5-level severity ranking consisting of: no

problems, slight problems, moderate problems, severe problems, unable to/extreme problems. The between-group mean difference in EQ-5D-5L change score at the 3-month follow-up will represent a secondary endpoint of the study.

7.1.7 Device- or Procedure-related Adverse Events at 3 Months

Adverse events (AEs) occurring within 90 days of treatment and that are adjudicated as definitely related or probably related to the device, or definitely related or probably related to the procedure will be included in this endpoint. The incidence of device- or procedure-related AEs within 90 days of treatment in each study group will represent a secondary endpoint of the study.

7.2 ADDITIONAL OUTCOMES

Additional outcomes of the study will include:

- Median time to return to normal activities
- Median time to return to work
- BCTQ-SSS change at 2 weeks, 1 month, 6 months, and 12 months
- BCTQ-FSS change at 2 weeks, 1 month, 6 months, and 12 months
- Numeric Pain Scale change at 2 weeks, 1 month, 6 months, and 12 months
- EQ-5D-5L change at 2 weeks, 1 month, 6 months, and 12 months
- Device- or procedure-related AEs at 2 weeks, 1 month, 6 months, and 12 months
- Serious device- or procedure-related AEs at 2 weeks, 1 month, 3 months, 6 months, and 12 months

8. ADVERSE EVENTS

An AE is defined as any adverse change (i.e., *de novo* or preexisting condition) from the subject's baseline medical condition occurring after the initial procedural incision has been initiated. Any AE which resolved and then recurred will be reported as a separate AE. A prespecified listing of AEs will be documented on the Adverse Event eCRF.

8.1 SERIOUS ADVERSE EVENT

A serious adverse event (SAE) is defined as one that suggests a significant hazard or side effect, regardless of the relationship to the device or procedure. This includes, but may not be limited to, any event that:

- Results in death
- Is life threatening, or places the participant at immediate risk of death from the event as it occurred
- Requires or prolongs hospitalization
- Causes persistent or significant disability or incapacity
- Results in congenital anomalies or birth defects
- Is another condition which investigators judge to represent significant hazards

Important medical events may be considered serious by the investigator although they may not be immediately life threatening or result in death or prolong hospitalization. Such important medical events are those that may jeopardize the subject, require intervention to prevent one of the outcomes listed above, or result in urgent investigation.

SAEs should be reported to the study Sponsor as soon as possible (24 hours recommended), but no more than 10 working days after the date the site becomes aware of the event.

Sites are also required to adhere to the reviewing IRB requirements for reporting of SAEs.

8.2 UNANTICIPATED ADVERSE DEVICE EFFECT

An unanticipated adverse device effect (UADE) is any serious adverse effect on the health or safety of a subject, any life-threatening problem or death caused by, or associated with a device, if such effect, problem, or death was not previously identified in nature, severity, or degree of incidence in the investigational plan (e.g., ICF, Study Protocol, Instructions for Use (IFU), publications, etc.), or any other unanticipated serious problem associated with a device that relates to the rights, safety, or welfare of subjects.

If an unanticipated adverse effect associated with the device occurs, the investigator shall notify the Sponsor and the IRB as soon as possible.

The Sponsor will investigate the event and notify the FDA and all other participating IRBs and investigators. Should the Sponsor determine that an unanticipated adverse effect presents an

unreasonable risk to all participating subjects, the Sponsor will suspend the clinical investigation and notify all participating investigators, IRBs, country regulatory bodies and FDA.

8.3 RELATIONSHIP OF ADVERSE EVENTS TO THE DEVICE OR PROCEDURE

A description of how an AE relates to the study device or procedure will be reported on the Adverse Event CRF.

- A device-related AE is directly attributable to the device or to improper use of the device.
- A procedure-related AE is directly attributable to the procedure, irrespective of the device, including complications from anesthesia or other procedures incidental to the main procedure.

The relationship of the AE to the device or procedure will be determined by the Investigator using the following definitions:

- **Definite:** The AE follows a reasonable temporal sequence from the time of the index procedure, which includes AEs that occur during the index procedure or during the follow-up period.
- *Probable*: The AE follows a reasonable temporal sequence from the time of the index procedure, and the possibility can be excluded that factors other than the index procedure, such as underlying disease, concomitant drugs, or concurrent treatment caused the AE.
- *Possible*: The AE follows a reasonable temporal sequence from the time of the index procedure and the possibility of index procedure involvement cannot be excluded. However, other factors such as underlying disease, concomitant medications, or concurrent treatment are presumable.
- *Unlikely*: The AE has an improbable temporal sequence from the time of the index procedure, or such AE can be reasonably explained by other factors, including underlying disease, concomitant medication, or concurrent treatment.
- **Not related**: The AE has no temporal sequence from the time of the index procedure, or it can be explained by other factors, including underlying disease, concomitant medication, or concurrent treatment.

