8.6 INDEPENDENT MEDICAL REVIEWER

Evaluation and adjudication of all AEs will be performed on an ongoing basis by an independent medical reviewer. The independent medical reviewer will review AEs for AE classification, seriousness, and relationship to the device or procedure. Discrepancies between the investigational site and the independent medical reviewer will be handled by discussion, with the determination by independent medical reviewer serving as the final classification.

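### Section 8.3 defines Definite by timing alone, so among well-timed adverse events the written grades do not separate those counted in the 7.1.7 safety outcome from those not counted

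*Combined protocol and SAP*

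**What the plan says.** Section 8.3 gives five grades of relationship and introduces them with: "The relationship of the AE to the device or procedure will be determined by the Investigator using the following definitions". The three that matter most here are:

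- **Definite:** "The AE follows a reasonable temporal sequence from the time of the index procedure, which includes AEs that occur during the index procedure". The sentence goes on to include the follow-up period and adds no further condition.
- **Probable:** the same timing, "and the possibility can be excluded that factors other than the index procedure" caused the event.
- **Possible:** the same timing, with involvement of the procedure not excluded. It adds: "However, other factors such as underlying disease, concomitant medications, or concurrent treatment are presumable".

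Unlikely applies when timing is improbable **or** other factors can reasonably explain the event. Not related applies when there is no temporal sequence **or** other factors can explain it.

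Above the grades, 8.3 describes a procedure-related event as one "directly attributable to the procedure, irrespective of the device, including complications from anesthesia or other procedures incidental to the main procedure", and it uses the same direct-attribution wording for device-related events.

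Section 7.1.7 counts events within 90 days that are "adjudicated as definitely related or probably related to the device, or definitely related or probably related to the procedure". It stands in the list of main outcomes, and its own text calls the incidence a secondary endpoint. Section 8.6 says: "The independent medical reviewer will review AEs for AE classification, seriousness, and relationship to the device or procedure". Differences from the site are discussed, "with the determination by independent medical reviewer serving as the final classification". Section 10.5 compares incidence per subject with Fisher's exact test.

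**The concern.** On an ordered causality scale the top grade should be the hardest to reach. Here it is the easiest of the top three, because it drops the causal condition that the next grade imposes. 7.1.7 places its cut between Probable and Possible, so an event that is meant to fall below the cut also satisfies the grade at the top.

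Comparing safety is part of the trial's stated purpose. From the plan alone, a reader of the results could not tell whether a rate of definitely or probably related events covers only events with other causes excluded, or every event with plausible timing. Two competent graders, one literal and one following the evident order of the scale, could report different rates from the same events. The first grading is made at the site, where 6.4 says the treating physicians are not blinded. The documents do not say whether the independent reviewer knows the assignment.

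**Working it through.** The plan states no figure to reproduce here, so the check is one of logic.

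**Step 1: conditions.** Each 8.3 definition is expressed in three facts about an event: timing (reasonable, improbable, none), other causes (excluded, presumable, able to explain the event) and procedure involvement (excluded or not). An event that other factors can explain is taken to be one where other factors are presumable. The incoherent case, with other causes and the procedure both excluded, is left out. That leaves 5 combinations for each timing, and 3 × 5 = 15 in all.

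**Step 2: reasonable timing.**

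| Other causes | Procedure involvement | Grades met as written | Status under 7.1.7 |
|---|---|---|---|
| Excluded | Not excluded | Definite, Probable | Counted |
| Presumable | Not excluded | Definite, Possible | Both |
| Presumable | Excluded | Definite only | Counted |
| Explain the event | Not excluded | Definite, Possible, Unlikely, Not related | Both |
| Explain the event | Excluded | Definite, Unlikely, Not related | Both |

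All 5 meet Definite and 1 of 5 meets Probable. Three of 5 meet a counted and an uncounted grade at once. No row meets both Probable and Possible, so that line is drawn; the faulty overlaps are between Definite and the uncounted grades. In the third row an event is counted although involvement of the procedure has been excluded.

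**Step 3: improbable or no timing.** The remaining 10 combinations meet only Unlikely, Not related or both. None is counted.

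These are counts of logical cases, not frequencies of events.

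**Step 4: what one grading is worth.** With the arm sizes in 10.1, one subject whose only related event crosses the line changes incidence by 1/80 = 1.25 percentage points (CTR-US) or 1/40 = 2.5 (mOCTR).

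**Step 5: illustration with assumed counts.** The documents give no expected counts for this outcome. Assume 4/80 and 2/40 subjects with events graded Definite or Probable as intended (5% in each arm, two-sided Fisher p = 1.0), then add subjects whose events were meant as Possible:

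| Added (CTR-US, mOCTR) | Result | Fisher p |
|---|---|---|
| 4, 2 | 8/80 vs 4/40 (10% vs 10%) | 1.0 |
| 4, 6 | 8/80 vs 8/40 (10% vs 20%) | 0.16 |
| 0, 6 | 4/80 vs 8/40 (5% vs 20%) | 0.020 |

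At very low counts one subject can matter. For 0/80 vs 2/40, p = (40 × 39)/(120 × 119) = 0.109. For 0/80 vs 3/40, p = (40 × 39 × 38)/(120 × 119 × 118) = 0.035. In both cases every other table with the same totals is more probable, so the two-sided p is this single term.

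**The case against.** The best reply is that nobody would apply the scale literally. A literal Definite makes Probable and Possible redundant, which cannot be intended. Overlap between Definite and Probable is harmless because 7.1.7 counts both. The Probable and Possible conditions are properly distinguished, so a grader who follows the evident order gets a usable outcome. Section 8.3 speaks of direct attribution, and one independent reviewer has the final word on all events, which favours a consistent reading. The p-values above rest on assumed counts, and pairs close to 0.05 exist in any sparse Fisher comparison.

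Much of this stands as a limit on the practical effect. It does not repair the text. The direct-attribution wording is not carried into any grade. Applied as a gate before grading, it would be hard to reconcile with having Possible, Unlikely and Not related at all. Section 8.6 says who decides but names no criteria, and 8.3 addresses its definitions to the Investigator. The Adverse Event CRF is not among the documents, so whether it gives graders further guidance is unknown.

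A reader might go further and infer that the grades separate nothing. Step 3 shows otherwise: events with improbable or no timing are always outside. A reader might also infer that related-event rates will be inflated, or will favour one arm. The documents do not support that either, since they do not show how the reviewer will read the scale or how ambiguous events will divide between the arms.

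**Conclusion.** The definition of Definite is wrong as written and should be corrected. It is less demanding than Probable, it contains every Possible event, and it also takes in well-timed events that other factors explain. The failure is confined to events with reasonable timing. It affects a main outcome that 7.1.7 treats as a secondary endpoint and that the 10.1 sample size calculation does not mention.

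The conclusion rests on the wording of 8.3 and on the absence of any one-grade or precedence rule in the documents. The size and direction of any effect on the reported rates cannot be computed. Steps 4 and 5 show only how far a few gradings could move the comparison, not that misgrading will occur.

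**What to change.** In 8.3:

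- Reword Definite to require everything that Probable requires (reasonable timing and exclusion of other causes) plus a stated, stronger criterion for certainty. That criterion should not reuse the direct-attribution phrase. The opening bullets apply the phrase to every related event, so a Probable event would then fail the section's own definition of related while 7.1.7 counted it. If the sponsor prefers that phrase, the bullets must be reconciled with the grades.
- State that each event receives one grade only.
- State that an event for which other factors are presumable, or which they explain, cannot be graded Definite or Probable. The well-timed event with procedure involvement excluded then needs a named place among the uncounted grades, because at present it meets Definite alone.

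In 8.6, state that the independent reviewer adjudicates with these definitions.

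Separating Unlikely from Not related is optional, since neither is counted in 7.1.7.

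The cost is a few reworded sentences and possible re-review of events already graded. No new data collection is needed.

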8.4 DEVICE FAILURES, MALFUNCTIONS AND NEAR INCIDENTS

Device failures or malfunctions will be reported to Sonex Health by the clinical sites. If the failure or malfunction results in an AE, the event shall be reported to the Sponsor within two (2) working days after the Investigator becomes aware of the event and reported to the IRB (if required) within the IRB required timeframe. The device involved in the incident should be returned to the Sponsor for evaluation.

8.5 REPORTING OF ADVERSE EVENTS

AEs will be recorded on the Adverse Event CRF and described by (a) duration (onset and resolution dates); (b) relationship to the study device or procedure; (c) action taken to resolve the event; (d) outcome of the event; and (e) whether or not such event is considered to have been

serious. Additional information, such as procedural notes, treatment notes, or a signed clinical summary may be required as supporting documentation for the reported AE.

During the study, all deaths must be reported to the Sponsor within 48 hours and should also be reported on the End of Study CRF. A copy of the subject's death records, medical records for the events that led to the subject's death, and a death certificate (if available) should be provided.

Determination of whether a subject experienced an AE can be made in three different ways. First, an AE can be documented by the site during the study procedure. Second, a subject may report an AE directly via phone call to the investigative site. Third, an AE can be identified by the site during the review of the subject-uploaded wound healing images. If the site identifies a potential AE based on image review or is notified of a potential AE by the subject, confirmation of the AE will occur by a phone call with the subject or, if necessary, by asking the subject to return for a follow-up clinical evaluation.

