1. PROTOCOL SYNOPSIS

Title	Trial of Ultrasound guided carpal tunnel release versus Traditional Open Release (TUTOR)					
Purpose	To compare the safety and effectiveness of carpal tunnel release with ultrasound guidance (CTR-US) vs. mini-open carpal tunnel release (mOCTR) in patients with symptomatic carpal tunnel syndrome (CTS)					
Study Design	Multicenter randomized controlled trial of subjects with symptomatic CTS who will be randomized in 2:1 fashion to treatment with CTR-US or mOCTR					
Enrollment	120 subjects will be enrolled in the study and randomized (2:1) to CTR-US (n≈80) or mOCTR (n≈40)					
Visit	Post procedure remote subject-reported outcomes visits:					
Schedule	1-14 days; 1, 3, 6, and 12 months					
Clinical Sites	Up to 12 investigational sites located within the United States					
Inclusion Criteria	 ≥18 years of age Clinical diagnosis of unilateral or bilateral idiopathic CTS CTS-6 score ≥12 in target hand Absence of carpal tunnel symptoms in the contralateral hand that interfere with normal daily activities or work at the time of consent and are not anticipated to interfere with return to activities or return to work within at least 3 months post-operatively Median nerve cross-sectional area ≥10 mm² in the proximal carpal tunnel region of the target hand measured by diagnostic ultrasound Prior failure of one or more nonsurgical treatment options for the target hand (e.g., physical activity modification, bracing, splinting, corticosteroid injection) Subject agrees to complete follow-up questionnaires over a 12-month period Subject has a valid mobile phone number and email address to receive and answer follow-up questionnaires 					

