6.7 FOLLOW-UP ASSESSMENTS

A list of the study assessments performed by the investigational site at each study interval is provided in the table below.

Assessment	Baseline Screening	Procedure	Post- Op	Day 7	Day 14	1 month	3 months	6 months	12 months
Demographics	√								
Ultrasound median nerve cross-sectional measurement	٧								
CTS-6 (both hands)	1								
Randomization	√								
Procedure		√							
Image of incision		√							
Adverse events		√	1	1	1	1	√	√	√

A list of the patient reported outcomes provided by the patient at each study interval is provided in the table below.

Assessment	Baseline Screening	Procedure	Post-Op	Daily 1-14	1 month	3 months	6 months	12 months
Demographics	√							
Medical history	√							
BCTQ-SSS	√			√1	1	1	1	1
BCTQ-FSS	√			√1	√	1	1	1
EQ-5D-5L	√			√1	1	1	1	1
Numeric Pain Scale	√	√	√	1	1	1	1	1
Procedure		√						
Images of wound healing				$\sqrt{2}$	1	√	√	√
Return To Activities (RTA)				1	1	√	√	√
Return To Work (RTW)				1	√	√	√	√
Pain Medication	√	√	√	1	√	√	√	-√

¹Collected at 14-day evaluation

²Collected at Day 7 and Day 14

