6.7.1 Unscheduled Follow-up Visits

If subjects are seen for unscheduled visits because of an AE or additional hand surgery, appropriate Case Report Form(s), will be completed, if applicable.

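### The plan states no scheduled adverse-event question to subjects, so events that a wound photograph cannot show may be under-counted in the 90-day safety outcome

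*Combined protocol and SAP*

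**What the plan says.** Section 8.5 introduces ascertainment with "Determination of whether a subject experienced an AE can be made in three different ways" and then lists the ways:

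- site staff record the event while surgery is under way;
- the subject telephones the site about it;
- photographs sent in by the subject are reviewed, in the plan's words: "Third, an AE can be identified by the site during the review of the subject-uploaded wound healing images"

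A phone call, or a return for evaluation if needed, then confirms an event that the subject or the image review has already raised.

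Section 6.7 holds two schedules. The first is introduced by "A list of the study assessments performed by the investigational site at each study interval is provided in the table below". Its adverse-event row is ticked at the procedure, Post-Op, Days 7 and 14, and 1, 3, 6 and 12 months, with no method given. The second lists what the patient reports after surgery: BCTQ, EQ-5D-5L, pain, wound images, return to activities, return to work and pain medication. It has no adverse-event row. The synopsis calls the follow-up contacts "Post procedure remote subject-reported outcomes visits". Section 6.7.1 provides for case report forms where applicable: "If subjects are seen for unscheduled visits because of an AE or additional hand surgery".

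On the outcome, Section 7.1.7 states: "The incidence of device- or procedure-related AEs within 90 days of treatment in each study group will represent a secondary endpoint". The synopsis lists the same quantity among the main outcomes. It counts events of any type adjudicated as definitely or probably related, and Section 10.5 compares incidence per subject with Fisher's exact test.

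**The concern.** Safety is half of the stated objective, and Section 3 describes the aim of carpal tunnel release as decompression without injury to nearby neurovascular structures. The events that matter most for that aim leave no mark on the skin. If the site looks for adverse events on a schedule only through wound photographs, a wound problem is actively sought, while new numbness or weakness, or treatment obtained elsewhere, is recorded only if the subject gets in touch.

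Two things are at stake. The first is under-counting of non-visible events in both arms. The second is the comparison. Section 6.4 gives scars of 3-5 mm and about 3 cm and says that neither surgeons nor subjects can be blinded. If visible events form a larger share of the total in one arm, or if subjects in one arm call more readily, incomplete capture would not cancel out.

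**Working it through.** The documents give no adverse-event rates by arm or type for this trial and no capture rates. The only design calculation (10.1) concerns a standardised effect of 0.60. It reproduces: exact t-test power is 80.8% at 68 and 34, and 102/(1 − 0.15) = 120. It does not bear on this point; only the arm sizes of about 80 and 40 are used below.

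**Step 1. Set 6.7 beside 8.5.**

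| Time | Site adverse-event tick (6.7) | Scheduled route that 8.5 describes |
|---|---|---|
| Procedure | yes | site documentation |
| Post-Op | yes | none; no image is scheduled |
| Days 7 and 14 | yes | wound image |
| 1, 3, 6, 12 months | yes | wound image |

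From Day 7 the ticks fall exactly on the image times. Image review may therefore be all that the row means, but the Post-Op tick cannot be explained that way. The two sections do not say how a scheduled assessment is made.

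**Step 2. Look for another route to non-visible events.** The questionnaires record symptoms and function, but no rule turns a worsening score into an adverse-event query. The independent reviewer (8.6) and the safety board (8.7) work on events already reported.

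**Step 3. Effect on the comparison.** Let *R* be the true risk, *q* the share of events that are visible, and *s_v* and *s_n* the capture of visible and non-visible events. With one event per subject,

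observed rate = *R* × [*q* × *s_v* + (1 − *q*) × *s_n*].

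If *R*, *s_v* and *s_n* are the same in both arms,

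difference (CTR-US minus mOCTR) = *R* × (*q*₁ − *q*₂) × (*s_v* − *s_n*).

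This is zero when the mix is the same (*q*₁ = *q*₂), however poor *s_n* is.

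All inputs below are assumptions, with *s_v* = 0.90. Cells show observed CTR-US vs mOCTR in %, the difference in points, and the chance that Fisher's exact test at 80 vs 40 is significant in favour of CTR-US.

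| True visible + non-visible risk | *s_n* 0.90 | 0.70 | 0.50 | 0.30 |
|---|---|---|---|---|
| A: 5+5 in both arms | 9.0 vs 9.0; 0.0; 2.1% | 8.0 vs 8.0; 0.0; 2.1% | 7.0 vs 7.0; 0.0; 2.2% | 6.0 vs 6.0; 0.0; 2.3% |
| B: CTR-US 2+8, mOCTR 8+2 | 9.0 vs 9.0; 0.0; 2.1% | 7.4 vs 8.6; −1.2; 3.6% | 5.8 vs 8.2; −2.4; 6.4% | 4.2 vs 7.8; −3.6; 11.7% |
| C: CTR-US 5+15, mOCTR 15+5 | 18 vs 18; 0.0; 2.0% | 15 vs 17; −2.0; 3.9% | 12 vs 16; −4.0; 7.6% | 9 vs 15; −6.0; 14.4% |

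Worked cell, B at 0.50:

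- CTR-US: 0.02 × 0.90 + 0.08 × 0.50 = 0.058.
- mOCTR: 0.08 × 0.90 + 0.02 × 0.50 = 0.082.
- Expected subjects with a recorded event: 80 × 0.058 = 4.6 and 40 × 0.082 = 3.3, against 80 × 0.09 = 7.2 and 40 × 0.09 = 3.6 with 90% capture of both types.

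Swapping the mixes between arms in B or C reverses the sign of every difference.

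Reporting that differs by arm acts in the same way even with mix A. Non-visible capture of 0.50 with CTR-US and 0.70 with mOCTR gives 0.05 × (0.50 − 0.70) = −1.0 point, and the reverse gives +1.0.

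**The case against.** The strongest reply is that 8.5 says how events can be determined, not that no other way exists. The site table ticks an assessment at every time point, including Post-Op, where image review cannot be what is meant. Unscheduled visits are provided for. Further hand surgery within 3 months leads to withdrawal (6.8.2.1) and an End of Study form (6.9), so it has a recording path once the site knows of it. Symptoms, function and pain are measured repeatedly and compared between arms. The plan also does not say what subjects are told about calling.

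Much of this stands. A reader might infer that events can reach the record by three routes only; the site ticks and the unscheduled visits do not support that. A reader might also count persisting symptoms as missed events, but Section 8 defines an adverse event as an adverse change from baseline, which unchanged symptoms are not.

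The most tempting inference is that the comparison is biased in favour of CTR-US. The documents do not support it. The same routes apply in both arms, so uneven capture by event type means under-counting and nothing more unless mix or reporting differs by arm. The prior data cannot settle this: they come from a single-arm registry that recorded complications by chart review and reported one incomplete release (0.3%) and no infections.

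The gap itself is not answered. The ticks have no stated method, and the other safeguards act only once an event is known.

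**Conclusion.** The point holds as a gap in ascertainment. Followed as written, the plan's only described scheduled post-operative look for adverse events is a wound photograph, and 6.7 and 8.5 do not agree on, or do not explain, what the ticked site assessments consist of. Non-visible events may be under-counted in the 90-day outcome, and that matters for safety even when the arms are affected equally.

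Between-arm bias is possible, not shown. It needs a difference by arm in event mix or in reporting. Under assumed opposite mixes with equal true risk, it runs from 1.2 to 6.0 points towards CTR-US as non-visible capture falls from 70% to 30%. It is zero with the same mix, and of opposite sign with the mixes reversed. None of these rates can be checked against the documents.

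**What to change.** Add a short structured adverse-event screen to the ViedocMe questionnaires at Day 7, Day 14 and 1, 3, 6 and 12 months, worded identically in both arms. Four items are enough: wound problem, new or worse numbness or weakness, unplanned medical contact, further hand procedure. Any positive answer leads to the confirmation step that 8.5 already describes. List the screen as a fourth route in 8.5 and as a row in the patient-reported table in 6.7, and state what the site tick consists of, Post-Op included, so that the two sections agree. Reporting wound events and nerve or functional events separately by arm would show whether the mix differs.

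The cost is a few questionnaire items, a small amendment, some extra confirmation calls and occasional return evaluations. Counts will rise somewhat in both arms. If the screen starts during enrolment, ascertainment will differ before and after the amendment. The report should state the date of the change and the number of subjects in each arm followed under each method.
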